#### **5.4.3 Reporting Requirements for Pregnancies**

##### **5.4.3.1 Pregnancies in Female Patients**

Female patients of childbearing potential will be instructed to immediately inform the investigator if they become pregnant during the study or within 5 months after the last dose of study drug. A Clinical Trial Pregnancy Reporting Form should be completed and submitted to the Sponsor or its designee immediately (i.e., no more than 24 hours after learning of the pregnancy), either by faxing or by scanning and emailing the form using the fax number or email address provided to investigators. Pregnancy should not be recorded on the Adverse Event eCRF. The investigator should discontinue study drug

and counsel the patient, discussing the risks of the pregnancy and the possible effects on the fetus. Monitoring of the patient should continue until conclusion of the pregnancy. Any serious adverse events associated with the pregnancy (e.g., an event in the fetus, an event in the mother during or after the pregnancy, or a congenital anomaly/birth defect in the child) should be reported on the Adverse Event eCRF. In addition, the investigator will submit a Clinical Trial Pregnancy Reporting Form when updated information on the course and outcome of the pregnancy becomes available.

#### **5.4.3.2 Pregnancies in Female Partners of Male Patients**

Male patients will be instructed through the Informed Consent Form to immediately inform the investigator if their partner becomes pregnant during the study or within 90 days after the last dose of cobimetinib. A Clinical Trial Pregnancy Reporting Form should be completed and submitted to the Sponsor or its designee immediately (i.e., no more than 24 hours after learning of the pregnancy), either by faxing or by scanning and emailing the form using the fax number or email address provided to investigators. Attempts should be made to collect and report details of the course and outcome of any pregnancy in the partner of a male patient exposed to study drug. The pregnant partner will need to sign an Authorization for Use and Disclosure of Pregnancy Health Information to allow for follow-up on her pregnancy. After the authorization has been signed, the investigator will submit a Clinical Trial Pregnancy Reporting Form when updated information on the course and outcome of the pregnancy becomes available. An investigator who is contacted by the male patient or his pregnant partner may provide information on the risks of the pregnancy and the possible effects on the fetus, to support an informed decision in cooperation with the treating physician and/or obstetrician.

#### **5.4.3.3 Abortions**

A *spontaneous* abortion should be classified as a serious adverse event (as the Sponsor considers abortions to be medically significant), recorded on the Adverse Event eCRF, and reported to the Sponsor immediately (i.e., no more than 24 hours after learning of the event; see Section 5.4.2).

*If a therapeutic or elective abortion was performed because of an underlying maternal or embryofetal toxicity, the toxicity should be classified as a serious adverse event, recorded on the Adverse Event eCRF, and reported to the Sponsor immediately (i.e., no more than 24 hours after learning of the event; see Section 5.4.2). A therapeutic or elective abortion performed for reasons other than an underlying maternal or embryofetal toxicity is not considered an adverse event.*

*All abortions should be reported as pregnancy outcomes on the paper Clinical Trial Pregnancy Reporting Form.*

#### **5.4.3.4 Congenital Anomalies/Birth Defects**

Any congenital anomaly/birth defect in a child born to a female patient exposed to study drug or the female partner of a male patient exposed to study drug should be classified as a serious adverse event, recorded on the Adverse Event eCRF, and reported to the Sponsor immediately (i.e., no more than 24 hours after learning of the event; see Section 5.4.2).

#### **5.4.4 Reporting Requirements for Cases of Overdose, Medication Error, Drug Abuse, or Drug Misuse**

Overdose (accidental or intentional), medication error, drug abuse, and drug misuse (hereafter collectively referred to as "special situations"), are defined as follows:

- Accidental overdose: accidental administration of a drug in a quantity that is higher than the assigned dose
- Intentional overdose: intentional administration of a drug in a quantity that is higher than the assigned dose}
- Medication error: accidental deviation in the administration of a drug

In some cases, a medication error may be intercepted prior to administration of the drug.

- Drug abuse: intentional excessive use of a drug that may lead to addiction or dependence, physical harm, and/or psychological harm}
- Drug misuse: intentional deviation in the administration of a drug that does not qualify as drug abuse

In cases where drug is to be self administered by the patient, drug misuse could involve the drug being administered to someone other than the patient.}

Special situations are not in themselves adverse events, but may result in adverse events. All special situations associated with atezolizumab or cobimetinib, regardless of whether they result in an adverse event, should be recorded on the Adverse Event eCRF and reported to the Sponsor immediately (i.e., no more than 24 hours after learning of the event). Special situations should be recorded as described below:

- Accidental overdose: Enter the drug name and "accidental overdose" as the event term. Check the "Accidental overdose" and "Medication error" boxes.
- Intentional overdose: Enter the drug name and "intentional overdose" as the event term. Check the "Intentional overdose" box. If drug abuse is suspected, check the "Drug abuse" box. If drug abuse is not suspected, check the "Drug misuse" box.
- Medication error that does not qualify as an overdose: Enter the name of the drug administered and a description of the error (e.g., wrong dose administered, wrong dosing schedule, incorrect route of administration, wrong drug, expired drug administered) as the event term. Check the "Medication error" box.

- Medication error that qualifies as an overdose: Enter the drug name and "accidental overdose" as the event term. Check the "Accidental overdose" and "Medication error" boxes. Enter a description of the error in the additional case details.
- Intercepted medication error: Enter the drug name and "intercepted medication error" as the event term. Check the "Medication error" box. Enter a description of the error in the additional case details.
- Drug abuse that does not qualify as an overdose: Enter the drug name and "drug abuse" as the event term. Check the "Drug abuse" box.
- Drug abuse that qualifies as an overdose: Enter the drug name and "intentional overdose" as the event term. Check the "Intentional overdose" and "Drug abuse" boxes.
- Drug misuse that does not qualify as an overdose: Enter the drug name and "drug misuse" as the event term. Check the "Drug misuse" box.
- Drug misuse that qualifies as an overdose: Enter the drug name and "intentional overdose" as the event term. Check the "Intentional overdose" and "Drug misuse" boxes.
- Drug administered to someone other than the patient: Enter the drug name and "patient supplied drug to third party" as the event term. Check the "Drug misuse" box.

Each adverse event associated with a special situation should be recorded separately on the Adverse Event eCRF. If the associated adverse event fulfills seriousness criteria, the event should be reported to the Sponsor immediately (i.e., no more than 24 hours after learning of the event; see Section 5.4.2). Adverse events associated with special situations should be recorded as described below for each situation:

- Accidental overdose: Enter the adverse event term. Check the "Accidental overdose" and "Medication error" boxes.
- Intentional overdose: Enter the adverse event term. Check the "Intentional overdose" box. If drug abuse is suspected, check the "Drug abuse" box. If drug abuse is not suspected, check the "Drug misuse" box.
- Medication error that does not qualify as an overdose: Enter the adverse event term. Check the "Medication error" box.
- Medication error that qualifies as an overdose: Enter the adverse event term. Check the "Accidental overdose" and "Medication error" boxes.
- Drug abuse that does not qualify as an overdose: Enter the adverse event term. Check the "Drug abuse" box.
- Drug abuse that qualifies as an overdose: Enter the adverse event term. Check the "Intentional overdose" and "Drug abuse" boxes.
- Drug misuse that does not qualify as an overdose: Enter the adverse event term. Check the "Drug misuse" box.

- Drug misuse that qualifies as an overdose: Enter the adverse event term. Check the "Intentional overdose" and "Drug misuse" boxes.

As an example, an accidental overdose that resulted in a headache would require the completion of two Adverse Event eCRF pages, one to report the accidental overdose and one to report the headache. The "Accidental overdose" and "Medication error" boxes would need to be checked on both eCRF pages.

## **5.5 FOLLOW-UP OF PATIENTS AFTER ADVERSE EVENTS**

### **5.5.1 Investigator Follow-Up**

The investigator should follow each adverse event until the event has resolved to baseline grade or better, the event is assessed as stable by the investigator, the patient is lost to follow-up, or the patient withdraws consent. Every effort should be made to follow all serious adverse events considered to be related to study drug or trial-related procedures until a final outcome can be reported.

During the study period, resolution of adverse events (with dates) should be documented on the Adverse Event eCRF and in the patient's medical record to facilitate source data verification.

All pregnancies reported during the study should be followed until pregnancy outcome.

### **5.5.2 Sponsor Follow-Up**

For serious adverse events, adverse events of special interest, and pregnancies, the Sponsor or a designee may follow up by telephone, fax, email, and/or a monitoring visit to obtain additional case details and outcome information (e.g., from hospital discharge summaries, consultant reports, autopsy reports) in order to perform an independent medical assessment of the reported case.

## **5.6 ADVERSE EVENTS THAT OCCUR AFTER THE ADVERSE EVENT REPORTING PERIOD**

After the end of the adverse event reporting period (defined as 30 days after the last dose of study drug), all deaths, regardless of cause, should be reported through use of the Long-Term Survival Follow-Up eCRF. In addition, if the investigator becomes aware of a serious adverse event that is believed to be related to prior exposure to study drug, the event should be reported through use of the Adverse Event eCRF. However, if the EDC system is not available, the investigator should report these events directly to the Sponsor or its designee, either by faxing or by scanning and emailing the paper Clinical Trial Serious Adverse Event/Adverse Event of Special Interest Reporting Form using the fax number or email address provided to investigators.

## **5.7 EXPEDITED REPORTING TO HEALTH AUTHORITIES, INVESTIGATORS, INSTITUTIONAL REVIEW BOARDS, AND ETHICS COMMITTEES**

The Sponsor will promptly evaluate all serious adverse events and adverse events of special interest against cumulative product experience to identify and expeditiously communicate possible new safety findings to investigators, IRBs, ECs, and applicable health authorities based on applicable legislation.

To determine reporting requirements for single adverse event cases, the Sponsor will assess the expectedness of these events using the following reference documents:

- Cobimetinib Investigator's Brochure
- Atezolizumab Investigator's Brochure

The Sponsor will compare the severity of each event and the cumulative event frequency reported for the study with the severity and frequency reported in the applicable reference document.

Reporting requirements will also be based on the investigator's assessment of causality and seriousness, with allowance for upgrading by the Sponsor as needed.

[figure not shown]
## **6. STATISTICAL CONSIDERATIONS AND ANALYSIS PLAN**

[figure not shown]
This study is designed to explore the preliminary efficacy, safety, pharmacokinetics, immunogenicity, and biomarker of cobimetinib plus atezolizumab in seven patient cohorts with advanced solid tumors, including SCCHN, urothelial carcinoma, and RCC.

The primary analysis will be conducted once all patients in a particular cohort have been followed for a clinically meaningful period of time of approximately 16 weeks. The statistical results will be summarized and presented by cohort.

### **6.1 DETERMINATION OF SAMPLE SIZE**

The purpose of this study is for hypothesis generation only. No formal hypothesis testing or inference analysis is planned; hence, no power analysis is conducted. Approximately 20 patients are planned to be enrolled in Cohorts 1–6 with possible expansion up to approximately 40 patients in each cohort. Approximately 12 patients are planned to be enrolled in Cohort 7 (biopsy cohort). Therefore, up to approximately 250 patients in total are planned to be enrolled in this study.

## **6.2 SUMMARIES OF CONDUCT OF STUDY**

For all enrolled patients, enrollment, eligibility violations, and patient disposition will be summarized. Study treatment administration will be summarized for treated patients only.

### **6.3 SUMMARIES OF DEMOGRAPHIC AND BASELINE CHARACTERISTICS**

Patient demographics, baseline, and disease characteristics will be summarized descriptively using mean (standard deviation), median (interquartile range), or number and percent.

### **6.4 EFFICACY ANALYSES**

The analysis population for efficacy will include all patients enrolled in the study who received at least one dose of both study drugs.

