### 3.1.1.1 Cobimetinib and Atezolizumab Treatment Schedule

Cobimetinib will be administered orally at a starting dose of 60 mg QD starting on Day 1 through Day 21 followed by a 7-day rest of each 28-day cycle in all cohorts.

Atezolizumab will be administered by IV infusion at a fixed dose of 840 mg on Days 1 and 15 of each 28-day cycle. Patients in the biopsy cohort (Cohort 7) will begin dosing cobimetinib before atezolizumab and will receive 60 mg cobimetinib alone QD, starting on Day 1 through Day 14 for Cycle 1. Atezolizumab dosing (840 mg IV) will begin on Day 15 in Cycle 1 and will continue on Days 1 and 15 of every cycle thereafter. Both study drugs will be administered until unacceptable toxicity or loss of clinical benefit, as determined by the investigator, after an integrated assessment of radiographic and biochemical data, and clinical status (e.g., symptomatic deterioration such as pain secondary to disease). If one study drug is discontinued or temporarily withheld or dose reduced, the other study drug may be continued.

Because of the possibility of an initial increase in tumor burden caused by IC infiltration in the setting of a T-cell response (termed "pseudoprogression") with atezolizumab containing treatment, radiographic progression per RECIST v1.1 may not be indicative of true disease progression. In the absence of unacceptable toxicity, patients who meet criteria for disease progression per RECIST v1.1 while receiving cobimetinib and/or atezolizumab will be permitted to continue study treatment if they meet all of the following criteria:

- Evidence of clinical benefit, as determined by the investigator following a review of all available data
- Absence of symptoms and signs (including laboratory values, such as new or worsening hypercalcemia) indicating unequivocal progression of disease
- Absence of decline in Eastern Cooperative Oncology Group (ECOG) Performance Status that can be attributed to disease progression

- Absence of tumor progression at critical anatomical sites (e.g., leptomeningeal disease) that cannot be managed by protocol-allowed medical interventions
- Patient's written consent to acknowledge deferring other treatment options in favor of continuing study treatment at the time of initial disease progression

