### **3.1.1.2 Tumor Assessments**

Tumor response will be evaluated by either CT scan or MRI scan according to RECIST v1.1, as determined by the investigator (see Appendix 3). Any evaluable and measurable disease must be documented at screening and re-assessed at each subsequent tumor evaluation. Immune-modified RECIST will also be evaluated at the same time (see Appendix 4), as determined by the investigator. Investigators will assess tumor response at 8-week intervals, regardless of any dose delays or treatment cycles.

Patients who discontinue treatment for reasons other than disease progression (e.g., toxicity) will continue scheduled tumor assessments until disease progression, withdrawal of consent, study termination by Sponsor, or death, whichever occurs first.

In the absence of disease progression, tumor assessments should continue every 8 weeks regardless of whether patients start a new anti-cancer therapy, unless consent is withdrawn.

All patients will be followed for survival unless consent is withdrawn. In patients who are treated beyond progression, tumor assessments will be performed until discontinuation of treatment.

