### **3.1.1.3.2 Biopsy Cohort (Cohort 7)**

Patients enrolled in Cohort 7, the biopsy cohort, must have at least two (preferably three) accessible lesions that meet the requirements specified in the eligibility criteria. Exceptions may be made if a patient has only one lesion that allows multiple biopsies following discussion with Medical Monitor. One pre-treatment, two on-treatment biopsies, and possibly one post-progression biopsy will be performed. If more than one biopsy will be obtained from one lesion, the lesion should be large enough to permit successive biopsies  $\geq 1$  cm apart. Investigators are strongly encouraged to obtain two on-treatment biopsies as described below. At a minimum, the biopsy obtained between Day 10 and 14 of Cycle 1 should be obtained to test for possible immunologic effects of cobimetinib alone.

Patients in the biopsy cohort will undergo biopsies according to the following schedule:

- A pre-dose biopsy will be taken before Day 1, Cycle 1 (not required if a fresh biopsy was provided during screening)
- On Day 1, Cycle 1, patients will start treatment with cobimetinib alone
- A mandatory on-treatment biopsy will be obtained between Days 10 and 14 of Cycle 1
- Patients will receive their first atezolizumab dose on Day 15 of Cycle 1
- A mandatory second on-treatment biopsy will be obtained during Cycle 2, 4–6 weeks after the first dose of atezolizumab to assess the combined effects of cobimetinib and atezolizumab
- An optional, post-treatment biopsy will be obtained at the time of radiographic progression

Patients in the tumor biopsy cohort whose tissue sample is not evaluable may receive study treatment but may be replaced for the purpose of serial biopsy assessment.

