### **3.2 END OF STUDY AND LENGTH OF STUDY**

The study will end when all patients enrolled have been followed until death, withdrawal of consent, loss to follow-up, or the Sponsor decides to end the trial, whichever occurs first. Patients may continue study treatment until the development of progressive disease, unacceptable toxicity, and/or withdrawal of consent. Patients who discontinue study treatment for any reason will be followed for safety according to protocol, followed for disease progression, and followed for survival until death, withdrawal of consent, or loss to follow-up, whichever occurs first. Patients who start a subsequent anti-cancer treatment after study treatment discontinuation will be followed for survival as well as disease progression, per protocol.

The total length of the study, from screening of the first patient to last patient, last visit (LPLV) is expected to be approximately 3 years.

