### **3.3.2.1 Rationale for the Biopsy Cohort (Cohort 7)**

Cohort 7 is designed to allow assessment of the biological effects of cobimetinib on immune therapy. In this cohort, in Cycle 1 only, cobimetinib will be given for 14 days before initiation of atezolizumab treatment. Biopsies obtained before treatment start and between Days 10 and 14 of cobimetinib monotherapy period will allow elucidation of the effects of cobimetinib on tumor immune contexture. Additional biopsies taken during the combination treatment period and at radiographic progression will support evaluation of the effects of combination treatment on the tumor microenvironment and the identification of potential mechanisms of resistance to combination therapy.

During Cycle 2 and all subsequent cycles, patients in Cohort 7 will receive cobimetinib 60 mg QD 21/7 and atezolizumab 840 mg IV Q2W, the same dose and schedule as in Cohorts 1–6.

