#### **4.3.2.2 Atezolizumab**

Atezolizumab will be given at a fixed dose of 840 mg by IV infusion on Days 1 and 15 of each 28-day cycle. A 28-day period is considered a treatment cycle.

Patients in the biopsy cohort, Cohort 7, will receive the first dose of atezolizumab of 840 mg by IV infusions on Day 15 of Cycle 1. Thereafter, they will receive atezolizumab 840 mg IV infusion Q2W on Days 1 and 15 of Cycle 2 and all subsequent cycles.

Administration of atezolizumab will be performed in a monitored setting where there is immediate access to trained personnel and adequate equipment and medicine to

manage potentially serious reactions. For anaphylaxis precautions, see [Appendix 7](#). Atezolizumab infusions will be administered per the instructions outlined in [Table 3](#).

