## **4.6 TREATMENT, PATIENT, STUDY, AND SITE DISCONTINUATION**

### **4.6.1 Study Treatment Discontinuation**

Patients must permanently discontinue study treatment if they experience any of the following:

- Disease progression (see Section 3.1.1 for dosing beyond progression)
- Symptomatic deterioration attributed to disease progression as determined by the investigator after integrated assessment of radiographic data, biopsy results, and clinical status
- Intolerable toxicity related to any study drug
- Any medical condition that may jeopardize the patient's safety if he or she continues study treatment
- Use of another non-protocol-specified anti-cancer therapy
- Pregnancy

Patients must provide written consent to acknowledge deferring any standard treatment options that may exist in favor of continuing treatment at the time of initial progression.

The primary reason for study drug discontinuation should be documented on the appropriate eCRF and patients will remain in the study for safety follow-up.

Patients who discontinue study treatment prematurely will not be replaced.

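### The both-drugs efficacy population in Section 6.4 leaves out Cohort 7 patients lost before their first atezolizumab dose on Day 15, although OS and PFS are counted from enrollment

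*Combined protocol and SAP*

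**What the plan says.** Section 6.4 sets one efficacy population for the whole study: "all patients enrolled in the study who received at least one dose of both study drugs". It gives Cohort 7 no exception and adds no all-treated sensitivity analysis.

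Cohort 7 starts the two drugs at different times. Section 3.3.2.1 states that "in Cycle 1 only, cobimetinib will be given for 14 days before initiation of atezolizumab treatment", and Section 4.3.2.2 that these patients "will receive the first dose of atezolizumab of 840 mg by IV infusions on Day 15 of Cycle 1". In Cohorts 1–6 both drugs start on Day 1.

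Section 6.4.1 makes ORR the primary endpoint in all cohorts. Section 6.4.2 analyses OS in all cohorts, summarises PFS and DCR by cohort, and starts the OS and PFS clocks at enrollment. Section 6.5 defines the safety population by a dose of study drug, without requiring both.

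Follow-up does not end with treatment. Section 3.1.1.2: "Patients who discontinue treatment for reasons other than disease progression (e.g., toxicity) will continue scheduled tumor assessments until disease progression". Section 3.2: "Patients who discontinue study treatment for any reason will be followed for safety according to protocol, followed for disease progression, and followed for survival".

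On replacement, Section 4.6.1 says "Patients who discontinue study treatment prematurely will not be replaced", and Section 4.6.2 says the same of patients who withdraw from the study. The one exception, in Section 3.1.1.3.2, covers Cohort 7 patients whose tissue is not evaluable; they "may receive study treatment but may be replaced for the purpose of serial biopsy assessment".

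**The concern.** In Cohort 7, entry to the efficacy analysis depends on something that happens about two weeks after the clock starts. For OS this is immortal time: no one in the analysis set can have died before the first atezolizumab dose. The same sentence has almost no such effect in Cohorts 1–6, so one rule gives two different populations in results that are presented side by side by cohort.

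The likely direction differs by type of loss:

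- Leaving out lead-in deaths biases OS and PFS upward.
- Leaving out lead-in deaths, or patients with no later response assessment, biases ORR and DCR upward.
- For patients who stop for toxicity and stay in follow-up, the direction is not fixed. Leaving out one with stable disease at 16 weeks lowers DCR; leaving out a long survivor lowers OS.

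The study scans and follows patients who stop treatment, so outcomes it collects would be missing from the efficacy results. A death in the lead-in would appear in the safety tables but not in OS.

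**Working it through.** **The plan's own figure.** Section 6.1 gives sizes but no power calculation. Six cohorts at the expanded size plus Cohort 7: 6 × 40 + 12 = 252, which agrees with the stated total of about 250. Cohort 7 is 12 of these.

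**Who is excluded.**

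1. Inclusion requires a dose of each drug (Section 6.4).
2. The first atezolizumab dose in Cohort 7 falls on Day 15 (Sections 3.3.2.1 and 4.3.2.2). Appendix 1 allows ±3 days for the visit and ±7 days for drug administration, so the gap may not be exactly 14 days, but it remains.
3. A patient who dies, withdraws or stops all treatment before that dose fails the definition. A patient who stops only cobimetinib need not: "If one study drug is discontinued or temporarily withheld or dose reduced, the other study drug may be continued" (Section 3.1.1.1).
4. A replacement under Section 3.1.1.3.2 adds another patient; it does not return the lost one to the analysis.

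**Deaths in the lead-in.** The documents give no loss rate. As an assumption, take exponential survival at OS medians *m* quoted in Sections 1.1.1 to 1.1.3, with 30.44 days per month:

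p = 1 − exp(−ln 2 × 14 / (m × 30.44)); expected deaths = 12p; P(at least one) = 1 − (1 − p)^12

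| Median OS (months) | Source | p | Expected of 12 | P(at least one) |
|---|---|---|---|---|
| 5.1 | SCCHN, investigator's choice | 0.0606 | 0.73 | 0.528 |
| 7.9 | UC, atezolizumab | 0.0396 | 0.47 | 0.384 |
| 9.7 | UC, nivolumab | 0.0323 | 0.39 | 0.326 |
| 25 | RCC, nivolumab | 0.0127 | 0.15 | 0.142 |

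**All causes of loss.** For an assumed total loss rate before Day 15, the chance that at least one of 12 is excluded is 22% at a rate of 2%, 46% at 5%, 72% at 10% and 86% at 15%.

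**Effect on ORR and DCR.** If *k* excluded patients are all non-responders, the estimate is multiplied by 12/(12 − k): 1.09, 1.20 and 1.33 for k = 1, 2 and 3. With assumed counts and the Clopper-Pearson intervals that the plan uses:

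| Quantity | All 12 kept | One excluded |
|---|---|---|
| ORR, non-responder excluded | 2/12 = 16.7% (2.1 to 48.4) | 2/11 = 18.2% (2.3 to 51.8) |
| DCR, patient without control excluded | 5/12 = 41.7% (15.2 to 72.3) | 5/11 = 45.5% (16.7 to 76.6) |
| DCR, patient with control excluded | 5/12 = 41.7% (15.2 to 72.3) | 4/11 = 36.4% (10.9 to 69.2) |

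The ORR shift is 18.2 − 16.7 = 1.5 percentage points, against an interval 48.4 − 2.1 = 46.3 points wide.

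**Effect on median OS.** Under a constant hazard, conditioning on survival to Day 15 moves the median from *m* to *m* + 14/30.44 = *m* + 0.46 month. That is 0.46/5.1 = 9.0% of the shortest median used and 0.46/25 = 1.8% of the longest.

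**The case against.** The strongest reply is that the both-drugs set matches the objective. The study evaluates the combination, a patient who never receives atezolizumab has not had it, and the population is stated openly. An any-dose set would count some outcomes on cobimetinib alone. This is a good reason to keep the both-drugs analysis, but it does not reconcile a population fixed around Day 15 with a clock that starts at enrollment.

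A second reply is that little depends on it. Section 6.1 calls the study hypothesis-generating with no testing, expansion applies to Cohorts 1–6 only, and Cohort 7 exists mainly for biopsies. That stands and limits the severity. Estimates and intervals are nevertheless the study's only efficacy output.

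Third, lead-in losses would be partly visible: Section 6.2 summarises disposition for all enrolled patients, Section 6.4.1 reports the number analysed, and Section 6.5 reports all deaths. A reader could partly recompute ORR from these, but not the Kaplan-Meier results for OS and PFS.

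Fourth, the medians are borrowed. None comes from a mixed-tumor population resistant to anti-PD-1/PD-L1 therapy. Section 4.1.1.1 requires ECOG 0–1 and a life expectancy of at least 3 months, so a constant hazard from Day 1 probably overstates early deaths and the 0.46-month shift with them. On the same deaths-only figures there is a 47% to 86% chance of no lead-in death. This caveat stands.

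Finally, toxicity is an uncertain route to exclusion. Table 5 in Section 5.1.3.4 stops both drugs for Grade 4 diarrhea, but a footnote lets atezolizumab be considered again after recovery from an immune-related event. That footnote is written for resuming the drug, and it is unclear how it applies to a patient who has not started it. Death and withdrawal do not depend on this reading.

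**Conclusion.** The concern holds and is minor. As written, Section 6.4 conditions every Cohort 7 efficacy result on reaching the first atezolizumab dose, about 14 days after treatment starts, and no other section lifts that condition. This follows from the text alone and is certain.

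The size is not certain. It rests on assumed exponential survival, borrowed medians and illustrative response counts, with toxicity and withdrawal adding losses at an unknown rate. On those assumptions at most about one lead-in death would be expected among 12, and the resulting shifts are well inside the confidence intervals. The bias is upward where the lost patients die or have no later assessment, and of unknown sign where they stop treatment but stay in follow-up. The effect is confined to about 12 of about 250 patients, in a descriptive study.

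**What to change.** Amend Section 6.4 for Cohort 7 only:

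- Define the efficacy population as enrolled patients who received at least one dose of either study drug, which is the safety set already defined in Section 6.5.
- State that patients with no response assessment count as non-responders. This largely follows from Section 6.4.1 once they are in the denominator, but it is worth making explicit.
- Keep all PFS and OS events from enrollment.
- Report the both-drugs set as a supportive analysis, labelled as conditional on reaching atezolizumab.

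The any-dose set still conditions on a first dose, but it closes the 14-day gap.

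The cost is two or three sentences and one supportive table. No new data are needed and no treatment rule changes. Cohort 7 ORR may come out slightly less favourable.
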